Study Visit Schedule and Procedures	
Detailed information regarding the study procedures is outlined in Section 6.
 
All patients enrolled will be randomized to a minimum of 6 months of treatment in 1 of 4 treatment cohorts. On completion of the 6 months, patients will continue treatment within the same randomized cohort until the last patient reaches 6 months of exposure (for continuing safety assessments), with a maximal exposure period of 12 months. Refer to Section 3.4.2 for additional detail regarding End of Treatment period and scheduling of End of Treatment Visits.
 
The study for an individual patient will generally consist of the following periods:
 
• An up to 4-week screening period, including a up to 2-week qualification period following an at least 2-week diet stabilization period where appropriate• An up to 52-week treatment period during which Study Drug will be administered per assigned cohort by SC injection• A 13-week post-treatment follow-up period 
Patients in Cohorts A and B will receive up to 13 SC doses of ISIS 678354 or placebo every 4 weeks. Patients in Cohort C will receive up to 26 SC doses of ISIS 678354 or placebo every 2 weeks and patients in Cohort D will receive up to 52 SC doses of ISIS 678354 or placebo weekly. Patients will return regularly for outpatient visits throughout the treatment and post-treatment follow-up periods according to the Schedule of Procedures (Appendix A).

[figure not shown]
PROTOCOL SYNOPSIS *Continued*

Study Visit Schedule and Procedures Continued	Blood and urine samples will be collected regularly throughout the study for safety, efficacy, and PK analysis. Appendix B shows a list of analytes required for the study and Appendix C details the PK sample schedules.
Safety and Tolerability Evaluations	Safety and tolerability assessments include: adverse events, vital signs and weight, physical examinations, clinical laboratory tests, ECGs (including serial ECGs in a subgroup of patients undergoing serial PK sampling) and use of concomitant medications. Safety and tolerability results in patients receiving ISIS 678354 will be compared with those receiving placebo.

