6.1.2 Treatment Period

Treatment period is defined as the time between the first and the last doses of study drug plus one dosing interval. During the treatment period, patients will report to the study center for clinic visits. Patients will receive 10 mg doses of Study Drug administered by SC injection once every 4 weeks for up to 49 weeks in Cohort A, 50 mg doses of Study Drug administered by SC injection once every 4 weeks for up to 49 weeks in Cohort B, 15 mg doses of Study Drug administered by SC injection once every 2 weeks for up to 51 weeks in Cohort C, or 10 mg doses of Study Drug administered by SC injection once per week (weekly) for up to 52 weeks in Cohort D ([Section 8.1](#)).

Collection and measurement of vital signs, physical examination results, ECGs, clinical laboratory parameters ([Appendix B](#)), ISIS 678354 plasma concentrations, immunogenicity and biomarker samples, AEs and concomitant medication/procedure information will be performed according to the Schedule of Procedures in [Appendix A](#).

Extensive Pharmacokinetic (PK) Subgroup Only:

Within each cohort, a subgroup of approximately 10 patients, who will consent to extensive PK sampling, will undergo additional PK sampling, in what is referred to as the PK Subgroup in this study. Patients in this subgroup will have additional PK sampling time points in order to evaluate the plasma PK parameters of ISIS 678354. Patients in this subgroup will have additional visits to the clinic during the treatment period in order to collect blood samples for PK assessment ([Appendix C](#)).

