Safety assessments will be summarized by nominal visit as collected in CRF. For summary tables by nominal visit, only scheduled visits will be used. For multiple records at the nominal (scheduled) visit, the average will be used for continuous values, or the worst will be used for categorical values.

For summary tables of platelet counts by nominal visit, scheduled visits from central lab data and separately, from local lab data will be used. For multiple records at the nominal (scheduled) visit, the average will be used for continuous values, or the worst will be used for categorical values.

3.2.2 *Patient Population Analyzed*

The following analysis sets will be used for the analysis of data as described within each analysis set.

Screened Patients are defined as the patients who sign an informed consent form.

Randomized Patients are defined as the patients who receive a randomization assignment.

Full Analysis Set (FAS): All patients who are randomized and received at least 1 dose of Study Drug (ISIS 678354 or placebo). The FAS represents the practically-feasible intent-to-treat (ITT) population as delineated in International Conference on Harmonisation (ICH) Guideline E9. This population will be used for the analysis of efficacy.

Per Protocol Set (PPS): Subset of the FAS who received prior to the Primary Analysis Timepoint at least 5 monthly doses of Study Drug for patients randomized in Cohorts A and B, or at least 11 every 2-week doses for patients randomized in Cohort C, or at least 22 weekly doses for patients randomized in Cohort D, and who have no major protocol deviations that could compromise the interpretation of efficacy. Major deviations will be determined prior to unblinding for statistical analysis. This population will be used for supportive inferences concerning efficacy.

Safety Set (SS): All patients who are randomized and received at least 1 dose of Study Drug. This population will be used for all safety analyses.

PK Population: All patients who are randomized and received at least 1 dose of ISIS 678354, and have at least 1 evaluable concentration result post first dose. This population will be used for analysis of PK data.

PK Subgroup: A subset of PK population who will undergo additional PK sampling after dose administration on Day 1 and Week 21 (Cohorts A and B) / Week 25 (Cohorts C and D) to evaluate the plasma PK parameters of ISIS 678354.

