Patients in PK subgroup will also have additional ECGs conducted as indicated in [Table 4](#).

Table 4: Additional PK Sampling and ECG Schedule for PK Subgroup

Cohort	Additional PK Sampling	Additional ECGs
--------	------------------------	-----------------

Cohort A and B	Week 1 (1, 2, 4, 8, 24 hr post-dose), Week 21 (1, 2, 4, 8, 24, 48 hr post-dose), Week 22 (Anytime), Week 23 (Anytime)	Week 1 (1, 2, 4, 8, 24 hr post-dose), Week 21 (1, 2, 4, 8, 24 hr post-dose)
Cohort C	Week 1 (1, 2, 4, 8, 24 hr post-dose), Week 25 (1, 2, 4, 8, 24, 48 hr post-dose), Week 26 (Anytime), Week 27 (pre-dose)	Week 1 (1, 2, 4, 8, 24 hr post-dose), Week 25 (1, 2, 4, 8, 24 hr post-dose)
Cohort D	Week 1 (1, 2, 4, 8, 24 hr post-dose), Week 25 (1, 2, 4, 8, 24, 48 hr post-dose), Week 26 (pre-dose)	Week 1 (1, 2, 4, 8, 24 hr post-dose), Week 25 (1, 2, 4, 8, 24 hr post-dose)

PK-ECG Set: All patients who provide baseline ECG data and at least one post-baseline matched PK before onset of anti-drug antibody and ECG record. This population will be used to analyze the exposure-QTcF relationship. Patients determined to have a pacemaker rhythm will be excluded from the PK-ECG Set.

All primary and secondary efficacy endpoints will be assessed in the FAS and PPS, with the former being the basis for the primary efficacy analysis. All exploratory efficacy endpoints will be assessed in the FAS. All safety assessments will be performed on the SS. PK endpoints will be assessed in the PK Population and PK Subgroup as applicable.

Patients in randomization populations, FAS and PPS will be analyzed in the treatment group to which they were randomized. Patients in SS, PK Population, PK Subgroup, and PK-ECG Set will be analyzed in the group with actual treatment they received.

[REDACTED]

[REDACTED]

[REDACTED]

[REDACTED]

[REDACTED]

[REDACTED]

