Abnormalities of platelet counts: The number and percentage of patients falling in each of the following categories (using available central and local laboratory assessments) based on worst post-baseline assessments will be provided:

- Any 2 occurrences of platelet count < 140,000 cells/mm³
- Any single occurrence of platelet count < 100,000 cells/mm³
- Any 2 occurrences of platelet count < 140,000 cells/mm³ or any single occurrence of value < 100,000 cells/mm³

The nadir platelet count will be summarized by following categories:

- Decrease \geq 30% from baseline
- Decrease \geq 50% from baseline
- 100,000 cells/mm³ to < 140,000 cells/mm³
- 75,000 cells/mm³ to < 100,000 cells/mm³
- 50,000 cells/mm³ to < 75,000 cells/mm³
- 25,000 cells/mm³ to < 50,000 cells/mm³
- 0 to < 25,000 cells/mm³

All categories of abnormalities in platelet count will be summarized based on confirmed values for on-study period as well.

Abnormalities of renal function: The number and percentage of patients falling in each of the following categories (using available central and local laboratory assessments) based on confirmed worst post-baseline assessments will be provided:

- eGFR by CKD-EPI $>$ 25% decrease from baseline
- UACR $>$ 250 mg/g
- UPCR $>$ 0.5 g/g
- Serum creatinine increase of $>$ 0.3 mg/dL from baseline

3.7.5 12-Lead Electrocardiogram

ECGs will be performed in triplicate at the visits indicated in the Protocol Appendix A. Patients in PK Subgroup will have additional ECG conducted during the treatment period. Patients determined to have a pacemaker rhythm will be excluded from summary tables.

The ECG data include ventricular rate, PR interval, QRS duration, QT and corrected QT intervals. For the continuous variables, the average of measurements at a given visit will be used for analysis. For the continuous variables above, descriptive statistics (n, mean, standard error, standard deviation, median, P25, P75, minimum, maximum, and mean 95% CI) of the observed values, as well as the change from baseline to each nominal study visit, will be presented by treatment group and for pooled placebo in summary tables. The summary table will be presented in SS and in PK Subgroup separately. Scheduled visits will be used for all summary tables.

The number and percent of patients who have the following reported events will be tabulated by treatment group and for pooled ISIS 678354.

- Absolute QT/QTcF/QTcB $>$ 450 msec
- Absolute QT/QTcF/QTcB $>$ 480 msec

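### SAP 3.2.2 nests the PK Subgroup in an active-only population, so the PK Subgroup ECG summary planned in SAP 3.7.5 has an empty pooled-placebo column

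*Combined protocol and SAP*

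**What the plan says.** **The formal sets.** SAP 3.2.2 (Patient Population Analyzed) builds the PK Population from patients who "received at least 1 dose of ISIS 678354, and have at least 1 evaluable concentration result post first dose". It then defines "PK Subgroup: A subset of PK population who will undergo additional PK sampling after dose administration on Day 1", and a second serial-sampling occasion follows at Week 21 or Week 25 depending on cohort. The grouping rule in the same section is "Patients in SS, PK Population, PK Subgroup, and PK-ECG Set will be analyzed in the group with actual treatment they received".

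**The working meaning of the name.** Protocol 6.1.2 describes the group differently: "Within each cohort, a subgroup of approximately 10 patients, who will consent to extensive PK sampling". SAP 2.1.2 repeats this description and adds that these patients have extra ECGs. Neither place limits the group to active drug. Protocol 10.3 has an active-only PK Population but no PK Subgroup analysis set, so the nesting enters with the SAP.

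**The table.** SAP 3.7.5 presents continuous ECG variables "by treatment group and for pooled placebo in summary tables", and then says: "The summary table will be presented in SS and in PK Subgroup separately".

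**The intent.** Serial ECGs in the serial-PK patients are part of a listed safety endpoint (protocol 10.1.3, SAP 1.4.4). The protocol synopsis says: "Safety and tolerability results in patients receiving ISIS 678354 will be compared with those receiving placebo".

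**The concern.** One name is used for two groups, and the stricter meaning is the one written as an analysis-set definition. A programmer who builds population flags from SAP 3.2.2 will produce a PK Subgroup of treated patients only. When the ECG summary in SAP 3.7.5 is run on that flag, its pooled-placebo column is blank.

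The placebo patients who gave consent and attended for the serial recordings then do not appear in the one ECG summary restricted to the serially sampled patients. A reader of that table sees active-arm changes with no concurrent control from the same subgroup. If the problem is found only after unblinding, the repair becomes an unplanned change of population for a safety output.

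**Working it through.** There is no sample-size, power or alpha figure to reproduce. The check has two parts.

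**1. Set logic**
- The PK Population in SAP 3.2.2 is "All patients who are randomized and received at least 1 dose of ISIS 678354", with an evaluable post-dose concentration as well.
- The PK Subgroup is a subset of the PK Population.
- So every member has had at least one dose of ISIS 678354.
- Members are grouped by treatment actually received. A patient randomized to placebo who was given ISIS 678354 in error could enter the set, but would not ordinarily be counted as placebo.
- Placebo n in the PK Subgroup version of the SAP 3.7.5 table is therefore **0**. No other section adds placebo patients to the set.

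**2. Placebo patients expected among those actually sampled**

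Inputs:
- 4 cohorts of about 25 patients (protocol 3.3)
- 4:1 allocation within cohort, so 25 x 1/5 = 5 placebo and 20 active (protocol 4.2, SAP 2.2)
- about 10 consenting patients per cohort (protocol 6.1.2, SAP 2.1.2)
- post-dose ECGs at 1, 2, 4, 8 and 24 h on two occasions (SAP Table 4)

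Assumption: consent to extensive sampling is independent of arm. This is reasonable because patients and site staff are blinded (protocol 4.4).

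Results:
- Expected placebo per cohort: 10 x 5/25 = 2
- Expected in all: 4 x 10 x 0.2 = **8** of about 40
- With 8 or 12 consenting patients per cohort instead of 10: 4 x 8 x 0.2 = 6.4, or 4 x 12 x 0.2 = 9.6
- Chance that a given cohort's 10 include no placebo patient: C(20,10)/C(25,10) = 0.0565
- Chance of none in all four cohorts: 0.0565^4, about 0.00001
- Hypergeometric total over four cohorts: P(3 or fewer) = 0.0095 and P(12 or fewer) = 0.9875, so P(4 to 12) = 0.9875 - 0.0095 = 0.978
- Scheduled post-dose triplicates from the expected placebo patients: 8 x 5 x 2 = 80

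So the column should hold about 8 patients, very probably between 4 and 12, and the definition makes it 0.

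**The case against.** The best reply is that the intent can be recovered. SAP 2.1.2 introduces the PK Subgroup by consent within cohort and mentions the extra ECGs. The explicit pooled-placebo column in SAP 3.7.5 shows that the ECG table means that group, and a careful programmer would ask. This is fair as to intent, but it does not remove the contradiction. The section that defines analysis sets says something else, and that is the text a population flag is written from.

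The reply is stronger on consequences, and most of it stands:

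- A reader might infer that the placebo serial ECGs are lost. They are not. The same summary is produced in the Safety Set, which keeps every dosed placebo patient, and SAP 3.7.5 lists all ECG data. The 80 triplicates are missing from one table, not from the study.
- A reader might infer that post-dose QTcF has no placebo adjustment. SAP 3.7.5 already plans one: the exposure-response model subtracts the pooled-placebo mean change in QTcF, and that formula is not limited to the PK Subgroup.
- A reader might infer that a placebo comparison at matched hours after dosing is being destroyed. SAP 3.7.5 summarises by nominal visit, using the mean of the measurements at the visit. No section says the table is laid out by hour, so restoring placebo would not by itself give an hour-matched comparison. An argument from within-day variation in ECG intervals would also rest on knowledge the documents do not supply.
- A reader might infer that the PK-ECG Set has the same fault and needs placebo patients entered at concentration zero. That set is not nested in the PK Population, and the placebo-corrected change is defined only for treated patients. A zero-concentration rule would be a modelling choice, not a correction.

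**Conclusion.** The contradiction is real and comes from the SAP's own text, not from redaction or text extraction. SAP 3.2.2 cannot be applied as written and still fill the table that SAP 3.7.5 specifies. Its size is one empty column, n = 0 where about 8 placebo patients of about 40 are expected. The estimate assumes about 10 consenting patients per cohort, 4:1 allocation, and consent independent of the blinded arm.

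The effect is limited to one descriptive safety table. No hypothesis test uses it, the primary efficacy analysis is untouched, and ECG findings are not named among the dose-selection criteria in protocol 10.1.4. The documents do not support a claim that the trial lacks a placebo comparison for ECG. The point is still worth correcting, because a stated rule yields a wrong table for a listed safety endpoint and the correction needs no new data.

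**What to change.** In SAP 3.2.2 (Patient Population Analyzed):

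1. Add a Serial ECG Subgroup: all Safety Set patients, on ISIS 678354 or placebo, who consented to extensive sampling and have a baseline ECG and at least one post-dose serial ECG.
2. In SAP 3.7.5, name that subgroup, in place of the PK Subgroup, as the second population for the ECG summary.
3. Keep the active-only PK Subgroup for PK parameters. Distinguish it from the consent-based group in SAP 2.1.2, so that one name no longer covers both.

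Leave the PK-ECG Set and the QTcF model as they are. The change should be made before unblinding.

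The cost is a few sentences and one extra population flag. The drawback that remains is precision: about 8 placebo patients allow a descriptive comparison and no more.

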3.2.4 Baseline and Endpoint Definition

For platelet count data, central and local lab will be used in baseline derivation. For other lab data, only central lab will be used in baseline derivation.

Baseline for lipid panel is defined as the average of Day 1 fasting pre-dose assessment and the last non-missing fasting measurement prior to Day 1 pre-dose assessment. If 1 of the 2 measurements is missing, then the other measurement will be assigned as the baseline value. If both are missing, then the baseline will be set as missing. Note that if on Day 1, there are multiple pre-dose assessments, then the last assessment with non-missing value will be used as the Day 1 pre-dose assessment.

Baseline for platelet is defined as the average of all assessments prior to the first dose of Study Drug.

Baseline for ECG is the average of the triplicate taken on Day 1 pre-dose for ECG summary over time and abnormal ECG parameters tables. If only one or two assessments are available, the single assessment or average of the two assessments will be used. If ECG results on Day 1 pre-dose is missing, results at screening visit will be used as baseline.

Baseline for other measurements is defined as the last non-missing assessment prior to the first dose of Study Drug.

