8.5 Safety Monitoring Rules

Stopping rules are described below in [Section 8.6](#).

Please refer also to the “Guidance for Investigator” section of the Investigator’s Brochure.

For the purposes of safety monitoring Baseline is defined as the average of the pre-dose test closest to Day 1 and the Day 1 value itself.

In addition to the standard monitoring of clinical safety parameters, the following guidelines are provided for the monitoring of selected parameters chosen based on preclinical and clinical observations.

In case of discrepancy between the test results from 2 sources, such as between the central and local lab, safety-mandated action must be initiated based on the more critical (lower or higher, as relevant) of the 2 values.

Confirmation Guidance: At any time during the study (treatment or post-treatment follow-up periods), the clinical laboratory results meeting any of the safety monitoring criteria presented below must be confirmed by performing measurements (ideally in the same laboratory that performed the initial measurement) on new specimens prior to administering the next dose of Study Drug (ISIS 678354 or placebo). All new specimen collections should take place as soon as possible (ideally within 3 days of the initial collection).

In addition, as described in [Section 6.2.1](#) hematology labs should be sent in parallel to the central and local laboratory for analysis.

Stopping Rule Guidance: The Investigator may interrupt or permanently discontinue study treatment for any medical reason including changes in clinical laboratory results.

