8.5.2 Safety Monitoring for Renal Function

While on treatment all patients will have renal function tests monitored every 14 days (± 2 days) for the first 3 months of the study treatment, and monthly thereafter during the Treatment Period. Upon completion of the study treatment period, urine renal biomarkers will be monitored as per visit schedule in [Appendix A](#).

In the event of appearance of symptoms or signs consistent with renal dysfunction such as hematuria, polyuria, anuria, flank pain, new-onset hypertension, nausea and/or anorexia, renal function should be tested as soon as possible. Testing at a lab that is local to the patient is permissible for this purpose.

While on treatment during the course of the study, urinary surveillance will include urinalysis to include urine albumin/creatinine ratio (UACR), urine protein/creatinine ratio (UPCR) and

urinary red blood cells (RBCs), as well as serum creatinine and cystatin-C which will be monitored every 14 days (± 2 days). In addition, biomarkers of acute renal injury will also be measured every 14 days (± 2 days) ([Appendix B](#)).

The assessment of serum creatinine, cystatin-C, and urinalysis more frequently than every 14 days will be guided by consultation with a local nephrologist. Any decision taken by the Investigator to discontinue study medication will be made taking into account all available and relevant data. In addition, the decision to discontinue Study Drug may also be based on lesser changes in these parameters observed in isolation or in association with other renal-related abnormalities. Any decision taken to restart study medication will be made in consultation with the Study Medical Monitor taking into account all available and relevant data.

All renal function test results will be reviewed on an ongoing basis by the Medical Monitor.

All results of renal function tests must be reviewed promptly (within 48 hours of receipt) by the Investigator or the designee to ensure that the result has not met the stopping rules per [Section 8.6.2](#).

Lab alerts for abnormal renal tests will be issued for:

- estimated GFR (eGFR) (by CKD-EPI formula) decrease from Baseline $> 25\%$,
- urine albumin/creatinine ratio (UACR) $> 250 \text{ mg/g}$,
- urine protein/creatinine ratio (UPCR) $> 0.5 \text{ mg/mg}$, or
- increase in serum creatinine from Baseline $> 0.3 \text{ mg/dL}$

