8.6 Stopping Rules

Monitoring rules are described above in [Section 8.5](#).

For the purposes of stopping rules, Baseline is defined as the average of Day 1 pre-dose assessment and the last measurement prior to Day 1.

8.6.1 *Stopping Rules for Liver Chemistry Elevations*

In the event of confirmed laboratory results meeting any of the following criteria, dosing of a patient with Study Drug will be stopped permanently:

1. ALT or AST > 8 x ULN, which is confirmed
2. ALT or AST > 5 x ULN, which is confirmed and persists for \geq 2 weeks
3. ALT or AST > 3 x ULN (or the greater of 2 x Baseline value or 3 x ULN if the Baseline value was $>$ ULN), which is confirmed and total bilirubin $>$ 2 x ULN or INR $>$ 1.5
4. ALT or AST > 3 x ULN (or the greater of 2 x Baseline value or 3 x ULN if the Baseline value was $>$ ULN), which is confirmed, and the new appearance (i.e., onset coincides

with the changes in hepatic enzymes) of fatigue, nausea, vomiting, right upper quadrant pain or tenderness, fever, rash, or eosinophilia ($>$ ULN) felt by the Investigator to be potentially related to hepatic inflammation

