10.4 Definition of Baseline

Baseline for TG, apoC-III, TC, LDL-C, HDL-C, non-HDL-C, VLDL-C, apoB, apoA-I and other lipid measurements will be defined as the average of the pre-dose measurement on Day 1 and the last measurement closest to Day 1, prior to administration of Study Drug. The baseline for other measurements is defined as the last non-missing assessment prior to the first dose of Study Drug.

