A confirmed laboratory value is based on consecutive lab values performed on a different day to, but within 7 days (no matter central lab data or local lab data). If consecutive value is same or worse, then the initial value is confirmed. If the consecutive value is better, then the initial value is confirmed using consecutive value. If there is no retest within 7 days, then the initial value is presumed

confirmed. If there are multiple results on the same day (no matter central lab data or local lab data), then the worst value will be utilized in the analysis.

The following lab results will be graded based on Toxicity Grading Scale for Healthy Adult and Adolescent Volunteers Enrolled in Preventive Vaccine Clinical Trials (September 2007). Number and proportion of patients with shift from baseline to worst post-baseline values by toxicity grade will be tabulated for on-treatment and on-study periods. Post-baseline lab results are defined as any assessment taken after the first dose no matter central lab or local lab data. If a patient has no baseline value but has a post-baseline value, then the baseline assessment will be labeled as “unknown”. Likewise, if a patient has a baseline value but has no post-baseline value, then the worst value will be labeled as “unknown”. Shift tables for eGFR, ALT, AST and total bilirubin will be provided using original and confirmed values.

- Hemoglobin: shift from Baseline to minimum post-baseline value
- WBCs: shift from Baseline to minimum post-baseline value
- Platelets: shift from Baseline to minimum post-baseline value
- BUN: shift from Baseline to maximum post baseline value
- Creatinine: shift from Baseline to maximum post-baseline value
- eGFR: shift from Baseline to minimum post-baseline value
- Proteinuria: shift from Baseline to worst post-baseline value
- ALT: shift from Baseline to maximum post-baseline value
- AST: shift from Baseline to maximum post-baseline value
- Alkaline phosphatase: shift from Baseline to maximum post-baseline value
- Total bilirubin: shift from Baseline to maximum post-baseline value

eGFR will be graded using the following criteria:

- $\geq 90 \text{ mL/min}/1.73\text{m}^2$
- $\geq 60 \text{ mL/min}/1.73\text{m}^2$ to $< 90 \text{ mL/min}/1.73\text{m}^2$
- $\geq 30 \text{ mL/min}/1.73\text{m}^2$ to $< 60 \text{ mL/min}/1.73\text{m}^2$
- $\geq 15 \text{ mL/min}/1.73\text{m}^2$ to $< 30 \text{ mL/min}/1.73\text{m}^2$
- $< 15 \text{ mL/min}/1.73\text{m}^2$

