The number and percent of patients who stopped treatment because they met a protocol-defined safety monitoring rule(s) and stopping rule(s) (see Protocol Section 8.6 for details) will be tabulated by treatment group. A listing will be provided for patients who met protocol-defined safety monitoring rules and for patients who terminated treatment due to a protocol-defined stopping rule as well.

Additional investigation of abnormalities in liver chemistry, platelet counts, and renal functions will be performed for on-treatment and on-study periods as below.

Abnormalities in liver chemistry: The number and percent of patients falling in each of the following categories (using available central and local laboratory assessments) will be tabulated based on worst post-baseline assessments by treatment group and for pooled ISIS 678354.

- The higher of ALT > 3 x upper limit of normality (ULN) or ALT > 2 x Baseline
- ALT/AST > 3 x ULN
- ALT/AST > 5 x ULN
- ALT/AST > 8 x ULN
- ALT > 3 x ULN - ≤ 5 x ULN
- ALT > 5 x ULN - ≤ 8 x ULN
- Total bilirubin > 2 x ULN
- ALP > 2 x ULN and (baseline ALP < 2 x ULN or baseline ALP missing)

The number and percent of patients falling in each of the following categories based on confirmed worst post-baseline assessments will be tabulated by treatment group and for pooled ISIS 678354.

- ALT/AST > 8 x ULN, which is confirmed
- ALT/AST > 5 x ULN, which is confirmed and persist for at least 2 weeks
- ALT/AST > 3 x ULN (or the greater of 2 x Baseline value or 3 x ULN if the Baseline value was > ULN), which is confirmed and either:
 - Total bilirubin > 2 x ULN, or
 - INR > 1.5, or
 - Temporal association with symptoms of fatigue, nausea, vomiting, right upper quadrant pain or tenderness (PT: abdominal pain or abdominal pain upper), fever, rash, or eosinophilia (PT: Eosinophilia and the corresponding lab value >ULN within the interval of associated Eosinophilia start and end date); and where temporal will be defined as the report date of the confirmed laboratory parameter occurring within the interval of the associated adverse event start and stop dates

For patients having confirmed 3-fold or greater elevations above the ULN for ALT or AST, a listing of all ALT, AST, total bilirubin, INR, and alkaline phosphatase records will be provided.

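### Protocol 8.5.2 can call a renal retest negative while it still meets the alert, and SAP 3.7.4 can report an unrepeated eGFR or creatinine reading as confirmed

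*Combined protocol and SAP*

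**What the plan says.** **Alerts and retests.** Protocol 8.5.2 sets four renal alerts. Two are changes from baseline: an eGFR fall above 25% and a serum creatinine rise above 0.3 mg/dL. The other two, UACR above 250 mg/g and UPCR above 0.5 mg/mg, are absolute. Meeting any of them interrupts treatment and requires a repeat within 7 days. If the repeat lies within the normal range it is called negative, and the patient may continue after consultation with the medical monitor. Under Protocol 8.6.2 a confirmed abnormal result means interruption if another cause is found and permanent withdrawal if none is.

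**Baseline for the alerts.** Protocol 8.5: "Baseline is defined as the average of the pre-dose test closest to Day 1 and the Day 1 value itself". Protocol 8.6: "Baseline is defined as the average of Day 1 pre-dose assessment and the last measurement prior to Day 1".

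**Baseline for the analysis.** SAP 3.2.4: "Baseline for other measurements is defined as the last non-missing assessment prior to the first dose of Study Drug". Protocol 10.4 agrees: "The baseline for other measurements is defined as the last non-missing assessment prior to the first dose of Study Drug".

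**The table.** SAP 3.7.4 reuses the same eGFR and creatinine cut-offs for patients "falling in each of the following categories (using available central and local laboratory assessments) based on confirmed worst post-baseline assessments will be provided". Its confirmation rule reads "If there is no retest within 7 days, then the initial value is presumed" confirmed. Renal tests are scheduled every 14 days (±2) "for the first 3 months of the study treatment, and monthly thereafter during the Treatment Period".

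**The concern.** A normal-range test cannot tell whether a change from baseline has gone away. A patient with low baseline creatinine or high baseline eGFR can still be past the alert on retest and yet be labelled negative. What is at stake is renewed dosing where 8.6.2 calls for interruption or withdrawal. The expedited report that Protocol 9.3.3.1 attaches to the renal stopping rule could also be missed. The same retest could count as confirmed in the SAP table, so one patient could be negative for dosing and confirmed in the report.

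The table has a separate weakness. Its baseline differs from the one that triggers retests, so a reading can cross the SAP cut-off without firing an alert. Nobody is then required to repeat it, unless another alert or symptoms prompt a test, and the absence of a repeat is what makes it count as confirmed. Change in renal function is a named safety endpoint, and each active regimen has about 25 × 4/5 = 20 patients.

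**Working it through.** The documents give no figure to reproduce, no within-patient variability and no laboratory normal ranges. Those inputs are assumptions, shown as ranges.

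**1. Retest in range but still past the alert**

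*Creatinine.* With upper limit U, this needs baseline + 0.3 < retest ≤ U, so it is possible whenever baseline < U − 0.3: below 0.8, 0.9 or 1.0 mg/dL for U = 1.1, 1.2 or 1.3. Example: 1.05 − 0.70 = 0.35 > 0.3, in range for all three limits.

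*eGFR.* With lower limit L, it is possible whenever baseline > L/0.75: above 80 for L = 60, above 120 for L = 90. Examples: 1 − 65/90 = 27.8% (L = 60); 1 − 92/125 = 26.4% (in range even for L = 90).

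*Frequency (simulated; true creatinine mean 0.9, SD 0.15 mg/dL; CV 5–10%).* Among creatinine breaches that the retest still meets, with a true rise of 0.35–0.40 mg/dL, the retest reads in range in:

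| Assumed upper limit | Share in range |
|---|---|
| 1.1 | 11–16% |
| 1.2 | 25–36% |
| 1.3 | 45–60% |

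For a true 30% eGFR fall the share is 32–60% with L = 60 and under 1% with L = 90.

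**2. Unrepeated reading counted as confirmed**

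*Creatinine example.* Earlier value 1.00, Day 1 0.80, later reading 1.15 mg/dL.
- Protocol: 1.15 − (1.00 + 0.80)/2 = 0.25, no alert and no retest.
- SAP: 1.15 − 0.80 = 0.35, past the cut-off.

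*eGFR example.* Earlier value 70, Day 1 90, later reading 64.
- Protocol: 1 − 64/80 = 20.0%, no alert.
- SAP: 1 − 64/90 = 28.9%, past the cut-off.

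*Can a routine draw serve as the retest?* Draws 14 days apart with ±2-day windows are at least 14 − 4 = 10 days apart. Days 169 and 183 with ±3-day windows are at least 14 − 6 = 8 days apart. Neither falls within 7 days, so both example readings are presumed confirmed.

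*Frequency.* The simulation used 300,000 patients with no true change, the creatinine distribution above and log-normal error. eGFR was taken as proportional to creatinine raised to −0.7, −1 or −1.2 (assumed). There were 9 tests to Week 25: six at 14-day intervals to Week 13, then Weeks 17, 21 and 25. A retest exists only if either change-from-baseline alert fires on the two-value baseline. Patients counted by the SAP but not confirmed on the protocol baseline, either category, per 100:

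| Creatinine CV | Exponent −0.7 | −1 | −1.2 |
|---|---|---|---|
| 5% | 0.01–0.02 | 0.03 | 0.25 |
| 7% | 0.6 | 1.3 | 3.7–3.8 |
| 10% | 5.0 | 8.4 | 13 |

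Over 90% of these rest on one unrepeated value. For exponents −1 and −1.2, 0–2.2 per 100 are confirmed on the protocol baseline, and at most 0.8 per 100 of those are missed by the SAP. In a group of 20, the CV 7% row gives 0.6 × 0.2 = 0.12 to 3.8 × 0.2 = 0.76 patients, and the CV 10% row gives 1.0 to 2.6.

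**The case against.** **On the retest.** A reader might infer that medical monitor consultation is all that stands between such a patient and the next dose. The documents do not support that. Protocol 8.5.2 also has the Investigator review nephrotoxic medication, and review any decision to continue with the medical monitor and the DSMB's specialist consultant. It allows stopping on smaller changes, and 8.6.2 applies separately when the abnormality is confirmed. These safeguards are real, but they work from a definition of negative that does not fit the alert. The general guidance in Protocol 8.5 judges a retest by whether the stopping criterion is still met.

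**On an easy repair.** Simply replacing the normal-range test with the alert criterion would loosen safety. A UPCR retest of 0.48 would become negative, although entry required less than 0.25. For a true creatinine rise of 0.35 mg/dL, about 15–18%, 9–10% or 4–5% of initial alerts (upper limit 1.1, 1.2 or 1.3) would be newly cleared with a retest still above normal. This objection stands and shapes the fix.

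**On the table.** The SAP follows Protocol 10.4, so a reader who infers that it contradicts the protocol's analysis section would be wrong. The mismatch is with 8.5 and 8.6. Nor is this the only by-group view of confirmed renal values, because SAP 3.7.4 also gives eGFR shift tables on original and confirmed values. Patients who stopped under a protocol rule are tabulated by group, and "A listing will be provided for patients who met protocol-defined safety monitoring rules". Presuming confirmation errs toward counting events and would count missed retests whatever the baseline. All this limits the harm, but it does not make the label accurate for a reading that nobody repeated.

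**Conclusion.** Both defects are in the text.

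The retest wording matters more because it bears on dosing. It is an ill-fitting definition with partial safeguards around it, not an unguarded route back to treatment. How often it bites depends on the laboratory's limits: often for creatinine if the upper limit is 1.2–1.3, hardly ever for eGFR if normal means 90 or more.

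The table problem is a small labelling error. It is negligible at a creatinine CV of 5%, about 0.6–4 per 100 patients at 7% and about 5–13 per 100 at 10%, assuming no true change and the stated eGFR slopes. One or two such counts per group of 20 require a CV near 10%. A reader might infer a bias for or against a dose. The documents do not support that, because the rule is the same in every group and the extra counts are noise expected equally in all. Only the eGFR and creatinine rows are affected, since UACR and UPCR use absolute cut-offs.

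**What to change.** 1. **Protocol 8.5.2 and 8.6.2.** State that a retest which still meets any renal alert criterion is not negative, even if it lies in the normal range, and give confirmation the same meaning in 8.6.2. Keep the normal-range requirement as an added condition, so that UACR, UPCR and above-normal creatinine retests are not cleared more easily than now. Cost: one clarifying sentence.
2. **SAP 3.7.4.** For the two change-from-baseline renal rows, use the two-value baseline of Protocol 8.5 and 8.6. Keep the last-value baseline for the by-visit summaries. Show values with no retest within 7 days separately from retest-confirmed values. The split is needed as well as the baseline change, because missed retests would otherwise still count as confirmed. Cost: one derived baseline (the SAP already averages two values for lipids) and one row split.
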